##### Step 2 - Delta Adjustments

The imputed values for subjects who discontinued will be adjusted by adding Delta ( $\delta$ ) to the results from step 1. Delta-adjusted fully imputed datasets will be generated for different combinations of  $\delta$  values for active treatment group and placebo group as defined below:

- $\delta = 0$  to tipping point value of  $\Delta$  by incremental of 1 to active treatment only
- $\delta = 0$  to tipping point value of  $\Delta$  by incremental of 1 to active treatment; for control group,  $\delta =$  half of active treatment adjustment
- $\delta = 0$  to tipping point value of  $\Delta$  by incremental of 1 for both active treatment and placebo groups

##### Step 3 – Analysis and Pooling

For each  $\delta$  combination described in step 2:

- Run MMRM model for each set of the adjusted datasets, the p-values for testing the treatment difference will be obtained.
- Multiple imputation combining rules in PROC MIANALYZE will be applied to the MMRM

The delta adjustment method will be applied for two scenarios:

- To all subjects who discontinued due to ICE categories 4 and 5.
- To all subjects who discontinued, except those with a discontinuation reason that was not considered related to the study drug, ie. lost to follow-up.

## Analysis for Estimand 4:

For testing of the treatment benefit impacted by COVID-19, a turning point threshold will be explored based on PTG-200 treatment effect.

### 5.3.4. Subgroup Analysis

The consistency of treatment effect for the primary endpoint will be evaluated for the subgroups defined in Section 5.7.8. For each of these subgroups, the difference of experimental group vs placebo in the change from baseline in the CDAI score at Week 12 and the associated 90% confidence interval will be provided. The same data handling rules will be applied as the primary efficacy analysis.

### 5.3.5. Multiplicity Adjustment for Secondary Endpoints

Inferential hypothesis testing will be conducted in a hierarchical manner with the test on the primary endpoint conducted first. Major secondary endpoints will be conducted only if the primary analysis of CDAI change from baseline achieves statistical significance. Within the major secondary endpoints, the gatekeeping approach in conjunction with graphical multiplicity control procedures will be applied. All statistical significance levels are defined at a 2-sided alpha of 0.1.

## 5.4. Secondary Endpoint(s) Analysis

### 5.4.1. Key Confirmatory Secondary Endpoint

#### 5.4.1.1. Definition of Endpoint(s)

The major secondary endpoints include the following at Week 12:

- Change in the SES-CD from baseline
- Clinical response as measured by CDAI ( $\geq 100$ -point reduction from baseline in CDAI or CDAI  $< 150$ )
- Clinical remission rate as measured by CDAI (CDAI  $< 150$ )
- PRO-2 remission defined as abdominal pain (AP) mean daily score (AP component of the CDAI) at or below 1 AND stool frequency (SF) mean daily score at or below 3, ie, AP  $\leq 1$  and SF  $\leq 3$
- Endoscopic response (defined as at least a 50% improvement from baseline in the SES-CD)
- Endoscopic remission (defined as an SES-CD score  $\leq 2$ )

The (SES-CD) is a scoring system developed to provide a more granular evaluation of endoscopic disease severity in patients with Crohn's disease. It is constructed based on the evaluation of 4 endoscopic components across 5 predefined ileocolonic segments. The 4 endoscopic components within each segment are: the presence/ size of ulcers, the proportion of mucosal surface covered by ulcers, the proportion of mucosal surface affected by any other lesions, and the presence/ type of narrowing (also commonly referred to as strictures/ stenosis clinically). Each endoscopic component is scored from 0 to 3 for each segment, and a total score is calculated as a sum of all the component scores across all the segments, as outlined in [Attachment 4](#). The total SES-CD score ranges from 0 to 56.

Calculation of the SES-CD score:

Main approach (SES-CD calculated based on all segments available):

The total SES-CD score at a visit will be calculated based on all segments scored at the visit. If the total SES-CD score cannot be calculated (i.e., no segment is scored) at a visit, the total SES-CD score will be considered missing.

Alternative approach (baseline segments matched approach):

To calculate the SES-CD score at a visit, the sum of the segments that were present at baseline will be used. For segments that were present at baseline but missing post-baseline, the baseline score for the missing segment(s) will be carried forward. In the event that a segment is missing at baseline but non-missing at post-baseline, the non-missing post-baseline score is not used in the calculation of SES-CD.

The Week 12 SES-CD Total score will be calculated only if the participant has a Week 12 endoscopy and at least one segment is evaluable. For segments evaluated and scored at baseline but not at Week 12, associated baseline segment scores will be carried forward to calculate the Total SES-CD score at Week 12. Otherwise, the Week 12 Total SES-CD will be missing.

Participants who meet 1 or more treatment failure rules (as specified for the primary endpoint) before Week 12 will be considered not to be in clinical remission, clinical response or clinical-biomarker response, either based on CDAI or PRO-2. For endoscopic response, the same treatment failure rules will be applied as appropriate. Any missing values at week 12 will be considered as no responder/remitter.

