4. STUDY DESIGN

4.1. Overall Design

This ISA is designed to assess the effects of a predominantly gastrointestinal-restricted anti-IL-23R compound for moderately to severely active Crohn's disease. This 12-week Phase 2a study is focused on proof-of-concept and will assess the safety and efficacy of an orally administered high dose of JNJ-67864238 compared with placebo in participants with Crohn's disease. Since the inhibition of the IL-23 pathway has been validated as a mechanism for treating Crohn's disease, a high dose was chosen to assess the efficacy of a locally acting anti-IL-23 inhibitor.

The target population for this intervention cohort is defined in Section 4.1.2 of the Master protocol PLATFORMPACRD2001 (ie, men or women 18 to 75 years of age with moderately to severely active Crohn's disease of at least 3 months' duration, defined as a Crohn's Disease Activity Index (CDAI) score ≥ 220 but ≤ 450 at Week 0, with a Simplified Endoscopic Score for Crohn's disease (SES-CD) score ≥ 3 by central endoscopy read OR an elevated C-reactive protein (CRP; >0.3 mg/dL or 3.0 mg/L) or elevated fecal calprotectin (>250 μ g/mg). In this intervention cohort, however, participants with a screening SES-CD score <3 who have an elevated CRP or elevated fecal calprotectin will be limited to 20% of the participant population.

Participants may be biologic intolerant or refractory (Bio-IR) or biologic nonfailures (Bio-NF) populations as defined in Section 4.1.2 of the Master protocol PLATFORMPACRD2001.

A target of 90 Bio-IR and Bio-NF participants will be randomized to receive JNJ-67864238 CCI [REDACTED] or placebo in a 3:2 ratio using permuted block randomization, stratified by baseline CDAI score (≤ 300 , >300) and biological refractory status (Bio-IR, Bio-NF). The treatment arms for this study will be as follows:

- JNJ-67864238 CCI [REDACTED] (N=54)
- Placebo (N=36)

Of note, the sample size has been chosen to assess a level of efficacy consistent with that observed with systemically available biological therapies for Crohn's disease (Section 2.1 of this ISA).

There is 1 database lock (DBL) planned at the end of this intervention cohort. In addition, there will be a planned Interim Analysis (IA) to enable early termination of the intervention cohort if JNJ-67864238 (CCI [REDACTED]) is futile. Additional ad hoc IA(s) may be conducted if deemed necessary. No DBLs are planned for any of the IA(s).

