5.1. Inclusion Criteria

Each potential participant must satisfy all of the following Master PLATFORMPACRD2001 protocol and these ISA-specific criteria to be enrolled in the JNJ-67864238 intervention cohort.

Master PLATFORMPACRD2001 protocol inclusion criteria are listed below.

1. Male or female
2. 18 to 75 years of age, inclusive

Disease Characteristics

3. Have Crohn's disease or fistulizing Crohn's disease of at least 3 months' duration, with colitis, ileitis, or ileocolitis confirmed at any time in the past by radiography, histology, and/or endoscopy
4. Have active Crohn's disease, defined as a baseline CDAI score of ≥ 220 and ≤ 450
5. Have evidence of active ileocolonic Crohn's disease as assessed by:
 - a. An SES-CD score ≥ 3 at screening by central endoscopy reading
OR
 - b. An elevated screening CRP (>0.3 mg/dL or 3.0 mg/L) or an elevated screening fecal calprotectin (>250 μ g/mg)
6. A participant with a family history of colorectal cancer, personal history of increased risk of colorectal cancer, age >50 years, or other known risk factor must be up-to-date on colorectal cancer surveillance (may be performed during screening). Adenomatous polyps must be removed before the first administration of the study intervention.

7. A participant who has had extensive colitis for ≥ 8 years, or disease limited to the left side of the colon for ≥ 12 years, must either have had a colonoscopy to assess for the presence of dysplasia within 1 year before the first administration of the study intervention or a colonoscopy to assess for the presence of malignancy at the screening visit, with no evidence of malignancy

Concomitant or Previous Medical Therapies Received

8. Meet the following requirements for prior or current medications for Crohn's disease:
 - a. Has previously demonstrated inadequate response to, loss of response to, or intolerance to an approved biologic therapy (unless otherwise specified in the JNJ-67864238 intervention cohort specific criteria below, ie, anti-TNF α agents [eg, infliximab, adalimumab, certolizumab pegol], anti-IL-12/23 agents [eg, ustekinumab], or anti-integrin agents [eg, vedolizumab]), ie, the Bio-IR population (Appendix 2 of the Master protocol PLATFORMPACRD2001 [Definition of Inadequate Initial Response, Loss of Response, or Intolerance to TNF Antagonist Therapies (Infliximab, Adalimumab, or Certolizumab Pegol), Vedolizumab, or Ustekinumab] and Section 5.2 of this ISA)

OR

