### **5.3.2. Estimand**

#### **5.3.2.1. Primary Estimand (Estimand 1)**

The primary estimand uses a Composite Strategy that considers meeting the treatment failure (TF) criteria as an unfavorable outcome. This strategy aims to achieve an objective treatment effect.

The primary estimand, the main clinical quantity of interest to be estimated in the study, is defined by the following components:

**Treatment:** Oral tablets CCI [REDACTED] for a 12 week period

- Experimental: JNJ-67864238 (PTG-200), CCI [REDACTED]
- Control: Matching Placebo tablets CCI [REDACTED]

**Population:** Participants with moderately to severely active Crohn's disease, The target population consists of men or women 18 to 75 years of age with moderately to severely active Crohn's disease of at least 3 months' duration, defined as a CDAI score  $\geq 220$  but  $\leq 450$  at Week 0, with an SES-CD score  $\geq 3$  by central endoscopy read. Participants with a screening SES-CD score  $< 3$  can be randomized and received at least one study dose if they have an elevated CRP ( $> 0.3$  mg/dL or 3.0 mg/L) or elevated fecal calprotectin ( $> 250$   $\mu\text{g/g}$ ). Participants must have colitis, ileitis, or ileocolitis previously confirmed at any time in the past by radiography, histology, and/or endoscopy. Participants must be biologic intolerant or refractory (Bio-IR) or biologic nonfailures (Bio-NF) and must be on a stable dose of at least 1 protocol-permitted therapy for the treatment of Crohn's disease prior to baseline and not receiving any protocol-prohibited therapies. For more details and for a complete list of inclusion/exclusion criteria, please refer to the protocol.

**Variable (Endpoint):** Change from baseline in the CDAI score at Week 12. Participants who have intercurrent events in categories 1-3 (defined below) prior to the Week 12 visit will have their baseline CDAI score assigned, regardless of the observed data.

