#### Variables and Population-level Summary (for Estimands 5-10)

**Table 2: Variables and Population-level Summary for the estimand for each Major Secondary Endpoint**

Estimand	Variable (Endpoint)	Population-level summary
5	Change in the SES-CD from baseline (both main approach and alternative approach analyses will be performed )	Change from baseline in the SES-CD score at Week 12 or early withdrawal visit between experimental group and placebo.

6	Clinical response as measured by CDAI ( $\geq 100$ -point reduction from baseline in CDAI or CDAI $< 150$ )	Difference in percentage of subjects who achieved clinical response at Week 12 between experimental group and placebo.
7	Clinical remission rate as measured by CDAI (CDAI $< 150$ )	Difference in percentage of subjects who achieved clinical remission at Week 12 between experimental group and placebo.
8	PRO-2 remission defined as abdominal pain (AP) mean daily score (AP component of the CDAI) at or below 1 AND stool frequency (SF) mean daily score at or below 3, ie, AP $\leq 1$ and SF $\leq 3$	Difference in percentage of subjects who achieved PRO-2 remission at Week 12 between experimental group and placebo.
9*	Endoscopic response (defined as at least a 50% improvement from baseline in the SES-CD) (both main approach and alternative approach analyses will be performed )	Difference in percentage of subjects who achieved endoscopic response at Week 12 between experimental group and placebo.
10	Endoscopic remission (defined as an SES-CD score $\leq 2$ ) (both main approach and alternative approach analyses will be performed )	Difference in percentage of subjects who achieved endoscopic remission at Week 12 between experimental group and placebo.

\* For Endoscopic response, please refer to below prohibited medications for ICE category 2

- Immunomodulatory agents other than AZA, 6-MP, or MTX (including, but not limited to, 6-TG, cyclosporine, mycophenolate mofetil, tacrolimus, and sirolimus).
- Immunomodulatory biologic agents (including, but not limited to, TNF antagonists, natalizumab, ustekinumab, rituximab, vedolizumab). Ustekinumab is permitted in this study only in participants randomly assigned to ustekinumab and only as stipulated in this protocol.
- Experimental Crohn's disease medications (including, but not limited to, upadacitinib, filgotinib, ozanimod, etrolizumab, brazikumab, mirakizumab [formerly LY-3074828], risankizumab, GS-5745)
- Thalidomide or related agents.

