#### **5.4.1.3. Analysis Methods for the Estimands for the Major Secondary Endpoints**

The major secondary endpoints of clinical remission (either based on CDAI, SES-CD, or PRO-2), clinical response, endoscopic response, and clinical-biomarker response at Week 12 will be compared between PTG-200 group and the placebo group.

A logistic regression model will be used in the responder analyses with the treatment arm and population status (Bio-IR or Bio-NF), if applicable, as fixed factors, at 2-sided significance level of 0.1. In this model, baseline measurements may be included as covariates as appropriate. The change from baseline in the SES-CD score at Week 12 will be evaluated using MMRM model in comparing treatment difference by LS Mean (SD), LS mean (90% CI). P-Value was based on comparison with placebo model. And other statistical analysis as appropriate.

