**Table 5: Demographic and Baseline Disease Characteristic Variables**

Continuous Variables:	Summary Type
Age (years)	Descriptive statistics (N, mean, standard deviation [SD], median and range [minimum and maximum], and IQ range).
Weight (kg)	
Height (cm)	
Crohn's Disease Duration (yrs)	
CDAI	
PRO-2 (defined as the sum of the abdominal pain and stool frequency subscores of the CDAI score)	
SES-CD	
CRP Concentration (mg/L)	
Fecal Calprotectin (mg/kg)	
Categorical Variables	
Race ([White, Black or African American, Asian, American Indian or Alaska Native, Native Hawaiian or Other Pacific Islander, Other, Not Reported and Unknown])	
Sex ([Male, Female])	
Involved GI areas ([Ileum only, Colon only, Ileum and colon, Proximal gastrointestinal tract, and Perianal])	
Extra intestinal manifestations ([Absent, Present])	
Endoscopic disease severity (SES-CD score) ([Remission (0-2), Mild inflammation (3-6), Moderate inflammation (7-16) and Severe inflammation (>16)])	
Abnormal CRP (>3 mg/L) ([Yes, No])	
Abnormal fecal calprotectin (>250 mg/kg) ([Yes, No])	
Crohn's disease complications (Intra-abdominal abscess, Sinus tracts /perforation, Fistula, Bowel Strictureing]	

Study Day and Relative Day: Study Day 1 or Day 1 refers to the day of the first study agent administration on or after the randomization date. All efficacy and safety assessments at all visits will be assigned a day relative to this date.

Study day or relative day for a visit is defined as:

- Visit date - (date of Study Day 1) +1, if visit date is  $\geq$  date of Day 1
- Visit date - Date of Day 1, if visit date < date of Day 1

There is no 'Day 0'.

Baseline: Baseline is defined as the last observation prior to the first study agent administration unless otherwise specified.

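### Week 12 endoscopic remission counts participants who entered at SES-CD 0-2 and did not change, and adjustment for baseline SES-CD is only optional

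*SAP*

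**What the plan says.** **Entry.** Protocol 5.1, criterion 5, accepts either a screening SES-CD of at least 3 or "An elevated screening CRP (>0.3 mg/dL or 3.0 mg/L) or an elevated screening fecal calprotectin". Protocol 4.1 adds that, in this cohort, participants with a screening SES-CD below 3 "who have an elevated CRP or elevated fecal calprotectin will be limited to 20% of the participant population". The SAP's primary estimand population (5.3.2.1) says the same participants "can be randomized and received at least one study dose if they have an elevated CRP" or calprotectin, without repeating the cap.

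**Label.** SAP Table 5 tabulates baseline severity as "Endoscopic disease severity (SES-CD score) ([Remission (0-2), Mild inflammation (3-6" and so on upward. A score of 0 to 2 at entry is therefore already called remission.

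**Endpoint.** SAP 5.4.1.1 defines remission by the Week 12 score alone: "Endoscopic remission (defined as an SES-CD score" of 2 or less). Table 2 (Estimand 10) summarises it as "Difference in percentage of subjects who achieved endoscopic remission at Week 12 between experimental group and placebo". Neither place sets a baseline condition.

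**Analysis.** SAP 5.4.1.3 uses logistic regression with treatment and Bio-IR/Bio-NF status, then adds: "In this model, baseline measurements may be included as covariates as appropriate". Baseline SES-CD is not named there. It is also not a randomisation stratum (Protocol 4.1 and 6.3; SAP 1.2) or a listed subgroup (SAP 5.7.8).

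**The concern.** SES-CD takes whole-number values, so a screening score below 3 means 0, 1 or 2. That is exactly the range that scores as remission at Week 12. A participant who enters through the CRP or calprotectin route can be a remitter without any endoscopic change.

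Two things are at stake. First, the reported remission rates mix participants who reached remission with participants who were there at entry, and the reader cannot separate them. Second, baseline status is likely to be a strong predictor of this outcome. A test that ignores it is less sensitive, and chance imbalance between arms in the number of such entrants adds noise.

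**Working it through.** **1. Plan figures.** The documents state no rate or power for endoscopic remission. Their power figure is for CDAI, and it reproduces: 60 / (93 × √(1/36 + 1/54)) = 60 / 20.01 = 3.00; 3.00 − 1.645 = 1.35; power 0.91 against the stated 90%. The design inputs (54:36, two-sided 0.1) are therefore taken as given.

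**2. Size of the group.** 0.20 × 90 = 18 at most, with an expected split of 10.8 active and 7.2 placebo. Because randomisation does not balance SES-CD, the split is treated as hypergeometric (90, 18, 54):
- The between-arm difference in the share of such entrants has an SD of 8.7 points.
- A difference of at least 10 points in either direction has probability 0.29.
- The placebo arm has 8 or more of 36 (above 20%) with probability 0.43.

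Twenty per cent is thus the trial-wide share at the cap, not a ceiling for each arm.

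**3. Effect on the rates.** Let p be the remission rate at baseline ≥3 and q the proportion of 0-2 entrants still at ≤2 at Week 12. The overall rate is 0.8p + 0.2q. Assume p = 10% placebo and 25% active:
- all stay: 8 + 20 = 28% vs 20 + 20 = 40%, difference 12 points
- 80% stay in both arms: 8 + 16 = 24% vs 20 + 16 = 36%, difference 12
- 70% placebo and 85% active stay: 8 + 14 = 22% vs 20 + 17 = 37%, difference 15
- 60% and 85% stay: 8 + 12 = 20% vs 20 + 17 = 37%, difference 17

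In the first case, 20 of the 28 placebo points (71%) come from participants already at 0-2 on entry.

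**4. Power for remission.** 200,000 simulated trials per setting; chi-square test at two-sided 0.1, counted in favour of active; stratified test is Mantel-Haenszel on baseline ≤2 vs ≥3; Bio-IR/Bio-NF not modelled. Same assumed rates, 10% vs 25%:

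| 0-2 entrants staying ≤2 (placebo/active) | 18 entrants: unadjusted | ≥3 subset | stratified | 9 entrants: unadjusted | stratified |
|---|---|---|---|---|---|
| 100%/100% | 0.32 | 0.49 | 0.49 | 0.41 | 0.53 |
| 80%/80% | 0.33 | 0.49 | 0.41 | 0.42 | 0.50 |
| 70%/85% | 0.45 | 0.49 | 0.56 | 0.49 | 0.56 |
| 60%/85% | 0.54 | 0.49 | 0.64 | 0.54 | 0.61 |

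Other assumed rates with 18 entrants all staying (unadjusted / stratified): 5% vs 20%, 0.33 / 0.60; 15% vs 30%, 0.31 / 0.43; 10% vs 30%, 0.47 / 0.67. The stratified test was ahead in all 32 remission settings run (four rate pairs, 18 or 9 entrants, four staying patterns).

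**5. Type I error.** With 10% in both arms and equal staying rates, rejection was 0.101-0.109 unadjusted and 0.099-0.104 stratified.

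**6. Endoscopic response, for contrast.** With 18 entrants and 10% vs 25% at baseline ≥3, unadjusted / stratified power by assumed response in the 0-2 group (placebo/active) is: 0/0, 0.479 / 0.486; 10%/10%, 0.445 / 0.445; 20%/20%, 0.418 / 0.416; 20%/40%, 0.587 / 0.585. With 4 entrants at 20%/40% it is 0.580 / 0.569.

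**The case against.** **The SAP already leaves room.** Section 5.1 lists Cochran-Mantel-Haenszel tests, 5.4.1.3 permits baseline covariates, 5.5 mentions covariate-adjusted analyses if needed, and the subgroup list is open-ended. The unadjusted figures therefore describe the least favourable use of an open choice. This stands as a limit on size. But nothing requires baseline SES-CD to be used, and choosing covariates after seeing the data is what prespecification should prevent.

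**There are partial safeguards.** Treatment failures and missing Week 12 values count as non-remission, the supportive endpoint of at least a 3-point fall cannot be met from 0-2, and the baseline category is tabulated by arm. These help interpretation but do not change how an evaluable, unchanged 0-2 entrant is scored.

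**The Master protocol may settle it.** Protocol 9.3 and 9.4.3 defer populations and secondary endpoints to that document, which was not supplied. A baseline restriction there cannot be ruled out.

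**Dilution is not certain.** If treatment prevents worsening among 0-2 entrants, the difference need not shrink (15 or 17 points above), and the unadjusted test can beat the ≥3 subset (0.54 vs 0.49). This is a good reason to keep the full population for the formal test. Stratification still gained power in those settings.

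**A reader might extend the point to endoscopic response.** That endpoint is "Endoscopic response (defined as at least a 50% improvement from baseline in the SES-CD"), so an unchanged entrant at 1 or 2 is not a responder. The figures in step 6 show stratification moving power by about −1 to +1 point. The power argument does not carry over.

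**Conclusion.** The point holds for endoscopic remission (Estimand 10) and is worth considering; it is not a major flaw. At the cap, about 20 percentage points of the overall remission rate can reflect status at entry. Under the assumed 10% vs 25%, ignoring baseline SES-CD costs about 17 points of power if all 18 entrants stay at ≤2 (0.32 vs 0.49) and about 8 points if 80% stay (0.33 vs 0.41). The gain from stratifying shrinks with fewer such entrants. The remission and staying rates are assumptions, 18 is an upper limit, and Bio-IR/Bio-NF was not modelled.

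Three stronger inferences are not supported:
- That the comparison is biased or its error rate inflated: entrants at 0-2 are randomised like everyone else, and simulated type I error stays near 0.1.
- That no arm can carry more than 20 points of entry-status remission: the cap is on the whole cohort, and one arm can exceed it by chance.
- That the trial's main conclusions are affected: CDAI power and the success and futility rules do not use this endpoint, and it is tested formally only if CDAI is significant (SAP 5.3.5).

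**What to change.** Before unblinding, in SAP 5.4.1.3 and Table 2 for Estimand 10:

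1. Keep the full analysis set for the formal test, but make baseline SES-CD (≤2 vs ≥3) a required stratification factor in addition to Bio-IR/Bio-NF. A stratified Cochran-Mantel-Haenszel test, which SAP 5.1 allows, is suitable. If everyone in the 0-2 stratum stays at ≤2, a logistic term for that stratum is not estimable; the stratified test avoids this.
2. Also report endoscopic remission in full-analysis-set participants with baseline SES-CD ≥3. Stratifying recovers power but does not take entry-status remission out of the reported rates.

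For endoscopic response no mandatory stratification is proposed. A supplementary report at baseline ≥3 is optional there, and stating that 0 at baseline and 0 at Week 12 is non-response would be a minor clarification.

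The cost is SAP wording and one supplementary table. Baseline SES-CD is already collected at screening. The supplementary table covers fewer participants (90 − 18 = at least 72 if 90 are enrolled) and speaks only to those with an SES-CD of 3 or more at entry.

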#### **5.4.2. Supportive Endpoint(s)**

Other endpoints to be evaluated across all post-baseline visits as appropriate:

- Change in AP from baseline based on a 0 to 10 numerical rating scale (NRS)
- Change in number of daily loose or watery stools
- Changes from baseline in the CDAI, PRO-2 (the sum of AP and SF subscores of the CDAI score), PRO-3 (the sum of AP, stool frequency, and general well-being subscores of the CDAI score), C-reactive protein (CRP), and fecal calprotectin
- Clinical remission (CDAI <150), PRO-2 remission (AP  $\leq$ 1 and SF  $\leq$ 3), and clinical response based on CDAI
- Endoscopic improvement based on a reduction from baseline in the SES-CD score ( $\geq$ 3 points, 25%, 50%), (both main approach and alternative approach analyses will be performed)
- Endoscopic healing (defined as the absence of mucosal ulcerations), (both main approach and alternative approach analyses will be performed)
- Patient's Global Assessment of Crohn's Disease Activity
- Change from baseline in multivariate score of biomarkers measured in mucosal biopsy samples, whole blood, serum, and/or stool
- Change in PROs as measured by the PROMIS-29 score

ICEs will be handled by the same Estimands strategies as the primary Estimands strategies for the supportive secondary endpoints. Participants who do not return for evaluation or have missing AP or SF scores at Week 12 will be considered not to be in PRO-2 remission (ie, clinical remission measured by AP and SF). Participants who do not return for evaluations or have missing CRP or fecal calprotectin values at Week 12 will be considered not to be in clinical-biomarker response unless the non-missing values at Week 12 already confirm a clinical-biomarker response. Any missing values at week 12 will be considered as no responder/remitter.

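### The alternative SES-CD calculation drops segments first scored at Week 12, so in that analysis a participant with observed active disease can be counted as in endoscopic remission

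*SAP*

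**What the plan says.** SAP 5.4.1.1 gives two ways to compute the SES-CD.

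- **Main approach:** "The total SES-CD score at a visit will be calculated based on all segments scored at the visit".
- **Alternative approach (baseline segments matched):** "the sum of the segments that were present at baseline will be used". A matched segment not scored after baseline takes its baseline score. For a segment missing at baseline but scored later, "the non-missing post-baseline score is not used in the calculation of SES-CD".

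A further paragraph of 5.4.1.1 deals with the Week 12 total. It requires a Week 12 endoscopy with at least one evaluable segment, and it carries baseline scores forward for segments scored at baseline but not at Week 12. It does not say whether it belongs to the main approach, the alternative approach or both.

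Table 2 in SAP 5.4.1.2 notes for SES-CD change, endoscopic response and endoscopic remission that main and "alternative approach analyses will be performed". For remission (Estimand 10, SES-CD of 2 or less) the summary measure is "Difference in percentage of subjects who achieved endoscopic remission at Week 12 between experimental group and placebo". SAP 5.4.2 extends both approaches to a supportive endpoint: "Endoscopic healing (defined as the absence of mucosal ulcerations), (both main approach and alternative approach analyses will be performed").

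**The concern.** Matching segments makes sense when Week 12 is compared with baseline: a change or percentage change should rest on the same bowel segments at both visits. Endoscopic remission is different. It is a threshold on the Week 12 state, with no baseline term. Dropping a segment that was seen and scored at Week 12 removes direct evidence about that state, and it can only lower the score.

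Endoscopic remission is a major secondary endpoint, and healing of the mucosa is named in a secondary objective (SAP 1.1). An analysis that reports documented Week 12 disease as remission would be hard to defend in a study report, however few participants are involved. It would also weaken the alternative analysis as a check on the main one.

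**Working it through.** **Scale.** SAP 5.4.1.1 states "Each endoscopic component is scored from 0 to 3 for each segment" and "The total SES-CD score ranges from 0 to 56". Attachment 4 has five segments, so three components reach 5 × 3 = 15 each. Narrowing is capped at 11, because an impassable narrowing can be observed only once: 3 + 4 × 2 = 11. The total is 15 + 15 + 15 + 11 = 56, which reproduces the stated maximum. One segment can hold up to 4 × 3 = 12 points.

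**Worked example, scored with Attachment 4.**

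- Baseline: ileum not scored; right colon 1+1+1+0 = 3; transverse colon 1+1+1+0 = 3; left colon 0; rectum 0. Total 6.
- Week 12: all four colonic segments 0; ileum scored for the first time.

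| Week 12 ileum (ulcer size + ulcerated surface + affected surface + narrowing) | Main total | Remission, main | Alternative total | Remission, alternative |
|---|---|---|---|---|
| 1+1+0+0 = 2 | 2 | yes | 0 | yes |
| 1+1+1+0 = 3 | 3 | no | 0 | yes |
| 2+2+2+0 = 6 | 6 | no | 0 | yes |
| 3+3+3+0 = 9 | 9 | no | 0 | yes |
| 3+3+3+3 = 12 | 12 | no | 0 | yes |

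The classification reverses in every row where the ileum scores 3 or more. All five rows have ulcers present at Week 12. If the discard rule were carried over to healing, all five would be healed under the alternative approach and none under the main approach.

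**Does another rule repair this?**

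- The Week 12 carry-forward covers segments scored at baseline but not at Week 12, which is the opposite case. Here nothing is carried forward.
- The rule that missing Week 12 values count as non-remission is not triggered, because the alternative total is 0, not missing.
- No minimum set of baseline segments is required.

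**Direction.** If the Week 12 carry-forward applies to the main approach too, then main total minus alternative total equals the sum of the scores of segments seen only at Week 12. That sum cannot be negative, so the alternative could add remitters but never remove one. If the carry-forward belongs to the alternative alone, the alternative total can be higher or lower than the main total.

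**Size per participant.** With 54 active and 36 placebo participants, all dosed and analysed, one misclassified participant moves the arm's rate by 1/54 = 1.9 points or 1/36 = 2.8 points. The documents do not say how often a segment is scored only at Week 12. Purely as an illustration, one to three such participants in one arm would move its rate by 1.9 to 5.6 points (3/54) on active or 2.8 to 8.3 points (3/36) on placebo.

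**The case against.** The strongest reply is that this is not the main analysis. The main approach counts every segment scored at Week 12 and classifies the example participant correctly. Both analyses are to be performed, so a disagreement could be seen. That stands, and it limits the point to the alternative analysis.

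A second reply is that remission is defined through the SES-CD, and that matching is one declared way to compute it. Matching holds the assessed segments constant, and it is conservative where a diseased baseline segment goes unseen at Week 12. The conservative part is sound and worth keeping. It does not justify discarding an observed score, because carry-forward and discard are separate steps and only the first is needed for a Week 12 state.

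A third reply concerns healing. The discard sentence is written for the SES-CD calculation, and absence of ulcers is not a total score. This stands: for healing, the SAP leaves the application unspecified, and it would be wrong to say that it certainly counts ulcerated participants as healed.

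A reader might also infer a bias in favour of active treatment, on the idea that treatment opens segments that could not be passed at baseline. The documents do not support that. Exclusion criterion 1 in Protocol 5.2 removes symptomatic strictures and stenoses, which narrows that route, and segments may be missed at baseline in either arm for reasons unrelated to treatment.

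**Conclusion.** The point holds for endoscopic remission in the alternative analysis: as written, the rule classifies some participants with observed active Week 12 disease as remitters, and no other rule corrects it. For endoscopic healing it holds conditionally, if the discard rule is carried over; otherwise the method is simply not stated.

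The consequences are limited. The primary endpoint is a CDAI change, and the success and futility rules (Protocol 9.2.2; SAP Attachment 1) use change in CDAI and change in SES-CD, so no go or no-go criterion depends on this. A reader might infer that the trial's endoscopic remission result as a whole is unreliable; the main approach shows that it is not. The number affected cannot be computed from the documents. What can be said is 1.9 points per misclassified participant on active and 2.8 on placebo, assuming full arms of 54 and 36. The point rests on the wording of the rule, not on an estimated frequency or a difference between arms.

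**What to change.** 1. In SAP 5.4.1.1, limit the baseline-matched approach to SES-CD change, endoscopic response and endoscopic improvement.
2. For endoscopic remission and endoscopic healing, count every segment scored at Week 12, whether or not it was scored at baseline. As the alternative calculation for these two endpoints, carry the baseline score forward for segments not scored at Week 12. For healing, state this in terms of the ulcer findings by segment.
3. State which approach the Week 12 carry-forward paragraph belongs to. If it is meant for the main approach as well, step 2 would give the same score as the main analysis, so simply drop the alternative analysis for Estimand 10 and for healing.
4. Amend the notes in Table 2 (Estimand 10) and in SAP 5.4.2 (healing) to match.

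The cost is SAP wording and a small programming change, with no new data. Remission and healing rates in the alternative analysis may come out slightly lower, and for these two endpoints the set of segments would no longer be held constant between visits, which a Week 12 state does not require.
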